In a different pilot study, of Caucasian men due to undergo radical prostatectomy at MSKCC, we are addressing the question: is there a small peptide mass proteomic profile/pattern in blood that can distinguish men with a clinically insignificant/latent prostate cancer from men with more advanced pathological features? In the current study, we propose to investigate if men of both African-American and Caucasian ethnicity have a small peptide mass proteomic profile/pattern in blood that may distinguish those with prostate cancer from those without. We will obtain a pre-biopsy blood sample from all Caucasian men and men of African-American descent, who are undergoing prostatic biopsy as part of their routine care, because of suspicion of prostate cancer. Matrix-assisted laser-desorption/ionized (MALDI) time-of-flight (TOF) mass spectrometry (MALDI-TOF MS) can determine the presence and molecular mass of polypeptides in serum.⁵ We will then analyze whether those who have prostate cancer on biopsy have a different small peptide mass proteomic profile in blood to those who have a negative biopsy for prostate cancer.

We will also analyze if the proteomic profile can improve the predictive power of known serum biomarkers (PSA, hK2 and solubilized urokinase-receptor forms (su-PAR)) for prostate cancer

IRB
PB

Amended: 2/1/12

Memorial Sloan-Kettering Cancer Center IRB Protocol

IRB#: 08-114 A(4)

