2.0 OBJECTIVES AND SCIENTIFIC AIMS

2.1 Primary Objectives

- To determine if men with prostate cancer have a different proteomic profile than men without cancer. Cancer-free status will be confirmed by a re-biopsy at 6 months to reduce the biopsy false negative rate to less than 5 %.
- To determine whether the peptide proteomic profile can improve the predictive ability of known serum biomarkers (PSA (free and total), hK2 and su-PAR) for prostate cancer.

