Recent studies demonstrated that both serum hK2 levels and single nucleotide polymorphisms (SNPs) of the KLK2 gene were positively associated with prostate cancer both together and individually, however they did not positively correlate with each other.¹⁴ Thus, the relationship of the SNPs of KLK2 to serum levels of hK2 and prostate cancer remains unclear yet and requires further research. As part of the collection process of the serum samples, leucocyte DNA in the buffy coat is available for collection that would normally be discarded. This potential repository of DNA would allow future DNA genotyping to be performed to assess kallikrein gene expression. We do not plan to assess kallikrein gene expression as part of this protocol but future studies may be performed to identify changes in various genes that predict cancer risk in a representative population such as this cohort of patients. These future studies would require Institutional Review Board (IRB) approval and would be in accordance with New York State Civil Rights Law §79-1(3) (a). These DNA samples will be de-identified but there will be a coded link to the clinical information in a database.

We will examine whether the peptide proteomic profile can improve the predictive ability of known serum biomarkers (PSA – free and total, hK2 and su-PAR) for prostate cancer.

All this information should allow us to better stratify which patients at risk of having prostate cancer do require prostate biopsy and which may not. This should reduce the number of negative and unnecessary biopsies performed.

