The purple or lavender top/EDTA tube contains anti-coagulated venous blood. This allows anti-coagulated plasma to be separated immediately from blood cells. The cells, including buffy coat, will allow for DNA genotyping assessing kallikrein gene expression. The plasma will be analyzed for certain kallikrein-family protein forms (hK2, total PSA and free PSA) and soluble urokinase plasminogen activator receptor-forms.

As part of the collection process of the serum samples, leucocyte DNA in the buffy coat is available for collection that would normally be discarded. This potential repository of DNA would allow future DNA genotyping to be performed to assess kallikrein gene expression. We do not plan to assess kallikrein gene expression as part of this protocol but future studies may be performed to identify changes in various genes that predict cancer risk in a representative population such as this cohort of patients.

IRB
PB

Amended: 2/1/12

Memorial Sloan-Kettering Cancer Center IRB Protocol

IRB#: 08-114 A(4)

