In the search and evaluation of novel diagnostics, very sensitive and specific assays were developed to detect certain kallikrein-family protein forms and soluble urokinase plasminogen activator receptor-forms. Proteases and their regulators involved in tumor invasion and metastasis comprise molecules that are candidates as prognostic or diagnostic targets. Plasminogen activation on the cell surface is catalyzed by urokinase plasminogen activator (uPA), which is secreted as an inactive proenzyme that localizes on the cell surface by binding to a specific glyco-lipid anchored receptor, uPAR. Plasmin and other proteases, e.g. trypsin, activate matrix metalloproteases (MMPs). These are capable of degrading extra-cellular matrix including collagen type IV, which is a major basal membrane component, while the destruction of the basal membrane may be crucial to allow invading cancer cells to escape from the originating organ. An assay designed to assess the heterogeneity of fPSA-fractions detects only single-chain (proPSA+mature fPSA) without cross-reaction from multi-chain fPSA cleaved at Lys₁₄₅-Lys₁₄₆ (fPSA-N), and has shown that fPSA-N is significantly higher in blood from men with BPH than cancer cases. A very sensitive (detection limit \leq 3 pg/mL) and specific assay for hK2 (<0.05% cross-reaction to PSA) distinguishes organ-confined cancer from cancer with extra-prostatic extension, and is a significant predictor of pathological stage by multivariate logistic regression analysis. Assays were also developed to measure intact-suPAR, suPAR (II+III), and suPAR domain I in blood, as plasmin-activation on this receptor may be critical to tumor invasion, and as kallikreins may use the urokinase plasminogen activation proteins as key targets. Levels of suPAR domain I and suPAR(II+III) have been found to be higher in men with cancer than in men without cancer, also in men with tPSA levels \leq 10 ng/mL. Prediction of cancer (reported as concordance index) may be enhanced using levels suPAR-forms combined with fPSA-forms and hK2 (AUC=0.805) compared to a base model using tPSA and age (AUC=0.69).^{13, 15} However, it is vital to use anti-coagulated plasma, rather than serum, for these measurements as fPSA and fPSA-fractions are prone to undergo significant pre-analytical degradation in vitro unless the sample is rapidly separated from the blood cells (i.e. within less than 6 hours) and the sample is exposed to ambient or refrigerated temperatures for less than 24 hours.

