
Assay for tPSA and fPSA: Free and total PSA are simultaneously measured with a DELFIA Prostatus™ Dual-label assay (Perkin-Elmer Life Sciences, Turku, Finland) in an equimolar fashion, by an assay which fully cross-reacts with hK2. Limits of detection are 0.04 ng/mL for fPSA and 0.05 ng/mL for tPSA. CV for tPSA is 13.9% at 0.34 ng/mL, and 5.5% at 20.6 ng/mL. CV for fPSA is 17.9% at 0.10 ng/mL and 4.7% at 2.9 ng/mL.

Assay for single-chain fPSA-I. The assay for single-chain fPSA uses biotinylated MoAb

IRB
PB

Amended: 2/1/12

Memorial Sloan-Kettering Cancer Center IRB Protocol

IRB#: 08-114 A(4)

5A10 immobilized to streptavidin-coated wells. Calibrators or samples (50 µl/well) are added and Eu-labeled MoAb 4D4 is added, plates are washed, and signal is measured. Recombinant proPSA is used as calibrator. Detection limit is 35 pg/mL and CV is 8.8%.

Assay for hK2: The current assay for total hK2 (thK2) has been modified to improve precision and linearity at low levels. The capture antibody called MoAb 7G1 has limited cross-reaction to PSA, which is eliminated by adding PSA-blocking MoAb 2C1. Detection limit is 3pg/mL, within-assay CV ranges from 4.8% to 1.5% for low to high hK2 levels, between-assay CVs ranges from 11.6% to 5.5% for low to high hK2 levels.

Immunodetection of suPAR-forms: Full-length intact uPAR assay: MoAb R2 is used as capture IgG. Calibrator (recombinant intact suPAR), sample, or controls, in duplicates are diluted and added (100 µL/well) and incubated for 1 h. Plates are washed, Eu-labeled MoAb R3 (R3-Eu) is added, incubated, washed, and fluorescence signals are measured.

Full-length intact uPAR + domain II+III assay: Protocol as above except that Eu-labeled K1 (K1-Eu) is used as tracer MoAb instead of R3-Eu. Intact uPAR is used as standard material as the assay detects uPAR domain II+III and intact uPAR with the same affinity. uPAR domain I assay: R5 is used for capture, protocol as above except: Recombinant suPAR domain I (1-92) is used as standard, sample incubation for 2 hours, and 1 µM of peptide AE120 is added together with R3-Eu to block signal from intact uPAR.

Intra-assay variation (CV) for intact, intact plus domain II+III, and domain I assays in EDTA plasma is 5.6%, 3.9% and 7.8%; and in citrate plasma 7.9%, 3.3% and 4.8%.

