Prediction models for “cancer” or “no cancer” membership will be developed. The first 250 patients accrued will be used as a training set and the second 250 will be used as a validation set. As the optimal analysis methods for these types of experiments are undefined, at least three approaches will be evaluated. One simple approach that will be used is to build a score for each patient based on forward stepwise logistic regression. The second method that will be used involves a statistical technique called “boosting” that puts extra emphasis on correct assignment of difficult cases. This approach was shown to be useful in the analysis of proteomic data in an earlier study.¹⁶ This will be combined with a logistic regression approach. A third technique that will be used is called “logic regression”.¹⁷ Here, a search is made through a large subset of the many possible combinations of binary predictors (in this case bins) to build a good prediction rule. This will be straightforward when the data is binary, but it can be utilized for continuous data by setting optimal thresholds for the intensities. In Aim 2, proteomic data will be combined with known biomarkers (PSA and hK2) and compared to models with just the biomarkers. Therefore, for this analysis, the known biomarkers will be forced into models; for Aim 1, only proteomic data will be included. To prevent over-fitting of the training set, 10-fold cross-validation will be utilized in the modeling. The modeling results will be evaluated using the area under the ROC curve (AUC), and the best models will be validated on the validation set. Models will be constructed both with and without clinical variables such as age and family history.

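### The Aim 2 analysis lists PSA and hK2 only, while the second primary objective also names su-PAR; followed literally, the objective as worded is not tested

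*Combined protocol and SAP*

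**What the plan says.** The objective in Section 2.1 is to find out whether the profile can "improve the predictive ability of known serum biomarkers (PSA (free and total), hK2 and su-PAR) for prostate cancer". Section 3.0 repeats the panel as "known serum biomarkers (PSA – free and total, hK2 and su-PAR) for prostate cancer", and Section 1.0 speaks of the aim to "improve the predictive power of known serum biomarkers (PSA, hK2 and solubilized urokinase-receptor forms (su-PAR)) for prostate cancer". All three include su-PAR.

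Section 4.2 commits to the measurements: "The plasma will be analyzed for certain kallikrein-family protein forms (hK2, total PSA and free PSA) and soluble urokinase plasminogen activator receptor-forms". It describes three su-PAR assays and reports their precision: "Intra-assay variation (CV) for intact, intact plus domain II+III, and domain I assays in EDTA plasma is 5.6%, 3.9% and 7.8" percent. It also describes a separate assay for single-chain free PSA.

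Section 11.0 is the only place where the markers in the Aim 2 models are listed: "In Aim 2, proteomic data will be combined with known biomarkers (PSA and hK2) and compared to models with just the biomarkers". It adds that the known biomarkers are forced into the models. The sample size paragraph restates the Aim 2 comparison, but refers only to the known biomarkers, with PSA as an example, and to the standard biomarkers. It gives their AUC as about 0.8, without a source. The word su-PAR does not occur in Section 11.0.

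**The concern.** Aim 2 is a question of added value, so the comparator defines what is tested. A gain over PSA and hK2 is a different finding from a gain over PSA, hK2 and su-PAR. If some peptides carry information that su-PAR already carries, a comparator without su-PAR would credit that information to the proteomic profile.

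The protocol itself treats su-PAR as informative. Section 3.0 says that it improves prediction by the kallikrein markers in men having a biopsy. Section 4.2 reports: "Levels of suPAR domain I and suPAR(II+III) have been found to be higher in men with cancer than in men without cancer", and says that this also holds at total PSA of 10 ng/mL or less. Section 5.1 enrols men with PSA between 2 and 10 ng/ml.

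There is also a practical problem. An analyst working from Section 11.0 would leave su-PAR out, and one working from Section 2.1 would put it in. Both could claim to follow the protocol, and the choice could be made after the results are known.

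**Working it through.** **1. The marker lists side by side**

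| Place | Total PSA | Free PSA | hK2 | su-PAR |
|---|---|---|---|---|
| 1.0 Summary | PSA, form not stated | PSA, form not stated | yes | yes |
| 2.1 Primary objectives | yes | yes | yes | yes |
| 3.0 Background | yes | yes | yes | yes |
| 4.2 Plasma assays | yes | yes | yes | yes |
| 11.0 Aim 2 models | PSA, form not stated | PSA, form not stated | yes | **no** |

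Su-PAR is the only marker that drops out. Free PSA is a matter of clarification, because the summary also writes plain PSA for a panel that Section 2.1 spells out as free and total.

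**2. The plan's figure for Aim 2**

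Section 11.0 says that the combined model needs an AUC of at least 0.89 for 80% power against biomarkers at about 0.8. The two samples are treated as independent, type I error is 0.05 and the validation set is 250. Sidedness and the variance method are not stated.

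Inputs:
- Validation set 250, with 30% cancers (Section 11.0): 0.30 × 250 = 75 cancers and 175 non-cancers.
- Comparator AUC A0 = 0.80.
- The detectable AUC A1 solves A1 − A0 = (z_α + z_0.80) × √(V(A0) + V(A1)). The multiplier is 1.645 + 0.842 = 2.487 one-sided and 1.960 + 0.842 = 2.802 two-sided.
- V(A) = [A(1 − A) + (m − 1)(Q1 − A²) + (n − 1)(Q2 − A²)] / (mn), with m = 75 and n = 175. Hanley-McNeil uses Q1 = A/(2 − A) and Q2 = 2A²/(1 + A). The alternative takes Q1 and Q2 from an equal-variance binormal model.

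Example (Hanley-McNeil, one-sided): the standard errors are 0.0333 at 0.80 and 0.0246 at 0.903. Then 2.487 × √(0.0333² + 0.0246²) ≈ 0.103, and 0.80 + 0.103 = 0.903.

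**3. The same calculation with the cited su-PAR panel as comparator**

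Section 4.2 cites su-PAR forms "combined with fPSA-forms and hK2 (AUC=0.805) compared to a base model using tPSA and age (AUC=0.69"). Putting A0 = 0.805 in place of 0.80 gives:

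| Variance, sidedness | A1 at 0.800 | A1 at 0.805 | Shift |
|---|---|---|---|
| Binormal, one-sided | 0.892 | 0.896 | 0.004 |
| Binormal, two-sided | 0.902 | 0.905 | 0.003 to 0.004 |
| Hanley-McNeil, one-sided | 0.903 | 0.907 | 0.004 |
| Hanley-McNeil, two-sided | 0.914 | 0.917 | 0.003 to 0.004 |

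The shift is about 0.004 whichever method is used. The table does not confirm the planned 0.89. At 75/175 one variant rounds to 0.89 and the other three do not. Hanley-McNeil with an equal split of 125/125, one-sided, gives 0.888.

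**4. What cannot be computed**

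The documents give no AUC for PSA and hK2 without su-PAR, and nothing on the overlap between peptides and su-PAR. No figure for the effect on the Aim 2 result follows from them.

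**The case against.** The strongest reply is that the parenthesis is shorthand. Section 11.0 reuses the term known biomarkers, which Sections 1.0, 2.1 and 3.0 each spell out with su-PAR. The su-PAR assays are planned. Section 11.0 is loose about the list elsewhere, and plain PSA stands there for what the objective calls free and total PSA. The planning AUC of about 0.8 is also nearer to the cited 0.805, from a panel with su-PAR, than to the 0.69 cited for total PSA and age. This is plausible and lowers the weight of the point. It does not remove it. No text in Section 11.0 restores su-PAR, the 0.8 has no stated source, and even under the shorthand reading the plan does not say which su-PAR assays enter the models.

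Some stronger readings are tempting but not supported:
- A reader might infer that su-PAR was deliberately dropped, or that Aim 2 will certainly use the wrong comparator. The text does not settle the intent.
- A reader might take the step from 0.69 to 0.805 (0.115) as an upper limit on what su-PAR contributes. Section 4.2 does not say whether the 0.805 model keeps total PSA and age, so the two models may not be nested. Nor does it divide the step among free-PSA forms, hK2 and su-PAR.
- A reader might infer that the omission upsets the sample size. The shift of about 0.004 shows otherwise.

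**Conclusion.** The point holds as a contradiction between a primary objective and its analysis. Su-PAR is in the objective's panel and is to be measured, but it is absent from the only list of markers for the Aim 2 models. Followed literally, Aim 2 tests a gain over a smaller panel than the objective names.

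The mismatch in wording is certain. That the wrong comparator would actually be used is not, since shorthand remains possible. The size of any effect on the result is unknown and may be nil. The one quantity available, the rise of about 0.004 in detectable AUC, rests on a 30% cancer share, independent samples, 80% power, and 0.805 standing in for the full panel. The cited panel uses free-PSA forms and may not be identical to the objective's panel. The point should be fixed, but it does not call the design into question.

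**What to change.** - In Section 11.0, replace the parenthesis with the objective's panel: total PSA, free PSA, hK2 and su-PAR. Force the same set into both Aim 2 models, with and without the proteomic data.
- State which of the su-PAR and free-PSA assay forms described in Section 4.2 enter. The second su-PAR assay reads intact receptor and domain II+III together, so it overlaps the first. Fix the choice before any marker or peptide data are linked to biopsy outcome. The blinding in Section 11.0 covers only the computation of bins and intensities, so it does not supply this safeguard.
- Keep any comparison against PSA and hK2 alone as a labelled secondary analysis.
- In the sample size paragraph, say which panel the AUC of about 0.8 describes.
- If PSA and hK2 is the intended comparator, restate the objective to match.

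Cost: no added patients, and su-PAR is already to be assayed. Choosing the assay forms is an analysis decision and needs some thought. The comparator may be harder to beat. The forced-in terms rise from two on the literal list to at least four, with about 75 cancers in the training set (30% of 250).

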4.0 OVERVIEW OF STUDY DESIGN/INTERVENTION

4.1 Design

This study will enroll two groups of 250 patients who are to undergo prostatic biopsy as part of their routine medical care because of suspicion of prostate cancer (elevated PSA between 2 and 10 ng/ml, abnormal rectal examination, or both). The first group will contain 250 patients of African-American descent and the second will contain 250 Caucasian men. The patients (both African American and Caucasian) will be recruited at both centres - New York Presbyterian Hospital, Weill Medical College of Cornell University, Manhattan and SUNY Downstate Medical Center in Brooklyn.

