4.2 Intervention

Patients will undergo standard pre-biopsy, intra-biopsy and post-biopsy treatment. This is considered standard treatment and is not part of the research study. Positive biopsy rates in a screened population will be in the order of 25-40%.^{1, 2} False negative biopsy rate of 20% is expected in the cohort that we plan to accrue. To account for this we will recommend that any patient who still has an elevated PSA or an abnormal DRE 6 months

**IRB
PB**

Amended: 2/1/12

Memorial Sloan-Kettering Cancer Center IRB Protocol

IRB#: 08-114 A(4)

after a first negative biopsy should undergo a repeat biopsy at that time. Repeating the biopsy in such a high risk cohort reduces the false negative rate from 20% to less than 5%. This false negative rate of < 5% is accounted for according to the statistical analysis.

Routine histological examination of the tissue specimens is also considered standard of care and is not performed solely for research purposes. Pre-biopsy, patients will be asked to provide five tubes (40 mL) of blood for research purposes (two “tiger” top – red-black – SST-tube, two green top tubes, one purple or lavender top/EDTA tube). The red-black “tiger” top SST-tube will provide clotted blood where serum is separated from blood cells by a gel-coat after centrifugation, while the green top tube contains heparin as anticoagulant. MALDI-TOF MS-based peptide-profiling proteomics data generated so far on serum samples in [name] laboratory have shown that it is critical to minimize variability in pre-analytical work-up of each patient sample as conditions during processing of the blood significantly affects the contents and composition of their proteomics profile. The samples will undergo serum peptide profiling using MALDI-TOF MS¹² (see Appendix A for details of development of a serum protein profile) and LC-MS (Liquid Chromatography-Mass Spectrometry). Serum peptide profiling will be carried out at two different sites to examine reproducibility, (The [name] Laboratory at New York University (NYU) and the [name] Laboratory, Sloan Kettering Institute ie the NY Consortium). This is an established consortium. We distinguish two aspects of reproducibility: *analytical* reproducibility, that is, whether a proteomics machine produces similar peaks on repeated samples, and *inferential* reproducibility, whether a proteomics experiment produces similar conclusions when repeated (see Biostats section 11).

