6.0 RECRUITMENT PLAN

Patients will be recruited from the Urology Clinic at Department of Urology, SUNY Downstate Medical Center in Brooklyn, the Department of Urology, New York Presbyterian Hospital, Weill Medical College of Cornell University, Manhattan and from Department of Urology, Kings County Hospital,. We will prospectively enroll 500 patients in total, 250 African-American and 250 Caucasian patients referred to both hospitals for TRUS guided

IRB
PB

Amended: 2/1/12

Memorial Sloan-Kettering Cancer Center IRB Protocol

IRB#: 08-114 A(4)

prostate biopsy. Approximately 30% will be found to have histological evidence of prostate cancer on their biopsy (150 patients) and 70% (350 patients) will not. This is based on approximately 33% expected to be positive in the African-American samples³ and 25-30% expected to be positive in the Caucasian samples. We anticipate that accrual will be completed in two years.

Estimated breakdown of target population by race/ethnicity:

% Native American/Alaskan	0%
% Asian/Pacific Islander	0%
% Black Non-Hispanic	50%
% Hispanic	0%
% White Non-Hispanic	50%
% Other	0%

It is stated that taking part in this study is voluntary and patients have the right to withdraw at any time. Participation in the study will not have an impact on the clinical care patients receive.

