Sample size considerations for the prediction rules are based on the AUC. The methods used here were introduced by Pepe.¹⁸ Since the known biomarkers, such as PSA, give an AUC of approximately 0.8, our goal in Aim 1 is a prediction rule with an AUC of greater than 0.8. For the validation set of size 250, fixing the type I error rate at 0.05, the true AUC would have to be at least 0.86 to have at least 80% power. This is based on a one sample test. In Aim 2, we are comparing the AUC of combining the standard biomarkers with proteomic data to just using the biomarkers. In this case, the AUC of the biomarkers plus proteomic model would have to be at least 0.89 to have at least 80% power. This is a two sample test. While the data are paired, we follow Pepe’s recommendation¹⁸ to treat the samples as independent for sample size determination because the correlation is unknown without pilot data and treating the samples as independent is conservative.

In addition to prediction, the association between peak intensity and group membership (“cancer” vs. “no cancer”) will be evaluated for every bin using the Wilcoxon rank sum test or Fisher’s exact test, depending on whether the data is being treated as continuous or binary. Adjustment will be made for multiple comparisons using the false discovery rate methods of Benjamini and Hochberg.¹⁹ Finally, the data will be hierarchically clustered to examine whether there are distinct peptide patterns associated with subsets of samples.

IRB
PB

Amended: 2/1/12

Memorial Sloan-Kettering Cancer Center IRB Protocol

IRB#: 08-114 A(4)

The full set of 500 samples will be examined using the standard MALDI technique at MSKCC. Thus, the main prediction rules that will be reported will be for these samples using this method at this site. As there are three time points, three separate rules will need to be reported and compared as discussed below. In addition, all data sets will be simultaneously processed in order to get the same sets of bins for reproducibility comparisons. Two other MALDI methods and two LC-MS methods will be used on a subset. For each, the same subset of 100 malignant samples and 100 benign samples will be examined. The same analyses as on the full set will be undertaken, but here 50 of each will be used as a training set and 50 of each will be used as a test set.

Secondary Objectives:

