The proteomic profiles of Caucasian men and of African-American men will be compared to see if the same peaks that are predictive in one are predictive in the other. In addition, the AUCs for the two groups will be compared based on models that use all the data.²⁰ Finally, separate models will be built for the two groups and the AUCs will again be compared.

As mentioned in section 4, we distinguish two aspects of reproducibility: *analytical* reproducibility, that is, whether a proteomics machine produces similar peaks on repeated samples, and *inferential* reproducibility, whether a proteomics experiment produces similar conclusions when repeated.

The basic method for assessing analytic reproducibility will be through the concordance correlation coefficient (CCC)²¹ of the intensity estimates. This CCC is a measure of the agreement between two readings of the same sample via the variation from the 45 degree line through the origin. It is on the same -1 to 1 scale as the standard Pearson correlation. Since there are about 600 bins per sample, there will be 600 CCCs for every comparison. Therefore, we will compute summary statistics of the CCCs. These summaries will be based on all the bins and just the discriminating bins. Since the statistic is only pair-wise, different analyses will have to be done for the three time points, the two sites, and the two platforms (MALDI and LC-MS). The only comparison between the platforms will be between standard MALDI and standard LC-MS.

Inferential reproducibility will consist of two components: determination of whether the same peaks are discriminating and comparisons of the AUCs for the prediction of cancer or no cancer. These comparisons will be made for the same varying conditions as for analytic reproducibility. For the former, discriminating peaks will be identified using a variety of thresholds and the differences will be reported as summary statistics. For the latter, formal testing of differences in AUCs will be undertaken, as well as summary statistics. A question of particular interest will be whether the difference in the estimated AUC from the two sites using the standard MALDI platform is statistically significant.

IRB
PB

Amended: 2/1/12

Memorial Sloan-Kettering Cancer Center IRB Protocol

IRB#: 08-114 A(4)

The last two secondary aims involve collection of material for future studies and no current data analyses.

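### The per-bin cancer tests take no account of race, recruiting hospital or age, so a bin that tracks only one of these can be read as a cancer peptide; the likely effect is modest

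*Combined protocol and SAP*

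**What the plan says.** Section 11.0 (Primary Objectives) adds a bin-by-bin analysis to the prediction models. Association with group membership "will be evaluated for every bin using the Wilcoxon rank sum test" when the bin is treated as continuous, and by Fisher's exact test when it is treated as binary. The only further step is multiplicity control: "Adjustment will be made for multiple comparisons using the false discovery rate methods of Benjamini and Hochberg". No false discovery rate level is given. The secondary objectives in the same section put the number of tests in view: "Since there are about 600 bins per sample".

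Other sections describe who is being compared:

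- **Race quotas.** Section 4.1: "The first group will contain 250 patients of African-American descent and the second will contain 250 Caucasian men". The same section says that men of both races will be recruited at both centres.
- **Cancer rates.** Section 6.0 gives "approximately 33% expected to be positive in the African-American samples" and "25-30% expected to be positive in the Caucasian samples", with 150 cancers expected among 500 men.
- **Hospitals.** Section 1.0 presents the Brooklyn hospital as the source of African-American men and the Manhattan hospital as the source of Caucasian men. Sections 5.0 and 6.0 add Kings County Hospital. Recruiting hospital enters no analysis; the two sites compared in Section 11.0 are the laboratories.
- **Handling.** Section 4.2 warns that "conditions during processing of the blood significantly affects the contents and composition of their proteomics profile", and sets a common collection procedure in response.
- **Age.** Section 11.0 includes age in some prediction models. It is not used in the per-bin tests.

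**The concern.** A pooled two-group test asks whether a bin is distributed differently in men with and without cancer. If the two groups differ in racial mix, hospital mix or age, a bin that responds only to one of those factors will also differ between them. The difference is real in the sample but says nothing about cancer within a race, hospital or age band.

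Benjamini-Hochberg limits the share of chance findings in the list. It does not separate cancer-related differences from differences carried by another factor.

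What is at stake is how the list of flagged bins is interpreted. That list bears on the first primary objective, whether men with cancer have a different profile. The reproducibility work would not reveal the problem, because the laboratories, platforms and repeat runs all use samples from the same men. A bin that tracks race or age would be expected to repeat.

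**Working it through.** **1. The plan's own count.** Expected cancers = 250 × 0.33 + 250 × p, where p is the Caucasian rate.

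- p = 25%: 82.5 + 62.5 = 145
- p = 27%: 82.5 + 67.5 = 150
- p = 30%: 82.5 + 75 = 157.5

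The stated 150 is reproduced, and it implies p = 27%.

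**2. Racial imbalance between the groups.** The African-American share is 82.5 / cancers among men with cancer, and 167.5 / (500 − cancers) among men without.

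| p | Share, cancer | Share, no cancer | Difference |
|---|---|---|---|
| 25% | 56.9% | 47.2% | 0.0971 |
| 27% | 55.0% | 47.9% | 0.0714 |
| 30% | 52.4% | 48.9% | 0.0348 |

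**3. Per-test error for a bin that tracks race only.** Assume that the bin is shifted by 1 SD between races and has no cancer effect within race, and that all 500 men are tested. The 1 SD is not in the documents. The overall SD is about √(1 + 1²/4) = 1.118. A normal approximation gives z = (difference / 1.118) / √(1/cancers + 1/non-cancers), and error = P(|Z + z| > 1.96).

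- p = 25%: z = 0.0868 / 0.0986 = 0.88, error about 14%
- p = 27%: z = 0.0639 / 0.0976 = 0.65, error about 10%
- p = 30%: z = 0.0311 / 0.0963 = 0.32, error about 6%

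Simulation of the Wilcoxon test agrees: 14.6%, 10.1% and 6.1%. A separate simulation gave 13.5% at p = 25% and 5.6% at p = 30%. Tests stratified by race stayed at 4.3% to 5.6%, and strata of race by hospital also returned about 5%.

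**4. After Benjamini-Hochberg.** Assume 600 bins, a false discovery rate of 0.05 (the plan states none) and no true cancer bins. The chance that any bin is flagged should then be about 5%.

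- p = 25%, 1 SD shift: about 15% if 20% of bins track race, and about 32% if 50% do
- p = 27%, 1 SD shift, 20% of bins: about 7%, with a mean of 0.13 bins flagged
- p = 30%: near nominal

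These rest on 60 replicates per setting (150 at p = 27%), so they are approximate. Many true cancer bins would loosen the cut-off and let more race-linked bins through.

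**5. Age.** The documents give neither the discrimination of age alone nor any correlation between bins and age, so every input here is assumed. With a 3-year case-control difference, SD 8 years and bin-age correlation r, z = r × (3/8) / √(1/150 + 1/350).

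- r = 0.1: z = 0.0375 / 0.0976 = 0.38, per-test error 6.7%
- r = 0.3: z = 0.1125 / 0.0976 = 1.15, per-test error 21%

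After Benjamini-Hochberg, with 120 of 600 bins tracking age, the chance of any flag was:

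| AUC of age alone | r = 0.3 | r = 0.5 |
|---|---|---|
| 0.55 | 5% | 10% |
| 0.60 | 20% | 63% |
| 0.65 | 67% | 95% |

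Stratifying by age decile brought this to about 2% to 8%.

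**6. Hospital.** The documents give no race-by-hospital split and no cancer rate by hospital, so no figure can be computed.

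**7. Cost of stratifying.** With no race effect on the bin, simulated power was 84.3% pooled and 83.8% stratified by race and hospital, a loss of 0.5 percentage points.

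**The case against.** The strongest reply is that the tests are valid for the question they ask. The null is equal distribution in men with and without cancer, and a bin that tracks race or age does depart from it when race or age relates to cancer. The stated aim is to tell the two groups apart, which is a marginal question. That stands. A reader might infer that false discovery rate control fails or that a stated error rate is wrong. The documents do not support this: no level is stated, and the fault arises only when a flagged bin is read as a cancer peptide.

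A reader might also infer that race and hospital cannot be separated. Section 4.1 has both races recruited at both centres, and Section 4.2 sets a common handling procedure that is expected to keep differences between hospitals small. This reduces the hospital concern. It does not remove it, because the procedure allows a range of spin forces and one to six months before samples are collected from the hospitals.

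Race is partly examined elsewhere. The secondary analysis checks whether peaks predictive in one race are predictive in the other, and a pure race marker would tend to be predictive in neither. This helps interpretation but leaves the primary bin list unchanged. The prediction models that include age do not change that list either.

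Finally, Section 11.0 places the per-bin tests alongside prediction, and the main evidence is the AUC in the validation set. That is correct and limits the weight of this point.

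**Conclusion.** The concern holds in a limited form. The per-bin tests ignore three factors that the documents themselves give reason to consider, and Benjamini-Hochberg does not address this. For race, per-test error is about 6% to 15% at a nominal 5%, and about 10% at the plan's own expected count, all for an assumed 1 SD shift. These are single-test figures and should not be read as the error rate of the final list, where the effect is small unless many bins track race strongly and the Caucasian rate is near 25%. Age may be the larger route, but its size depends entirely on assumed inputs.

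A reader might go further and infer that the reproducibility summaries are biased, because they use discriminating bins. The plan selects those at a variety of thresholds and does not say that they are the Benjamini-Hochberg list, and no bias in the concordance coefficients has been shown.

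**What to change.** In Section 11.0, replace the pooled per-bin tests with tests stratified by race and recruiting hospital, carried out before the false discovery rate step:

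- van Elteren (stratified Wilcoxon) for continuous intensities;
- stratified exact or Cochran-Mantel-Haenszel for binary bins.

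Report an age-adjusted version and the unadjusted list beside the result, so that bins which drop out are visible. State the false discovery rate level, and define the hospital strata so that Kings County Hospital has a place.

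Race and recruiting hospital are known at enrolment, and age is already a planned model variable, so no new samples or visits are needed. The cost is a little more analysis and the very small power loss shown in step 7.
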